7.3 Adverse Events and Serious Adverse Events

The study may result in adverse events related to medication side effects of solifenacin and high-dose VDS. Adverse events and serious adverse events will be classified based on the severity and intensity of the side effects.

7.4 Reporting Procedures

In the event of any adverse event, investigators will be notified within 24 hours.

7.5 Follow-up for Adverse Events

In the event of an adverse event, patients will be advised to seek medical advice immediately.

7.6 Safety Monitoring

As mentioned above.

8. INTERVENTION DISCONTINUATION

If any drug-related adverse effects or worsening of OAB symptoms in children during the intervention period occur, intervention measures should be discontinued. Otherwise, the intervention measures will start eight weeks after enrollment and will continue until the final data collection. At this point, study participants can withdraw their participation from this study.

9. STATISTICAL CONSIDERATIONS

9.1 General Design Issues

Objective: The aim of this randomized controlled trial is to examine the effectiveness and safety of high-dose VDS plus SU for managing OAB-dry symptoms in pediatric patients with low vitamin D levels (<35ng/mL).

Specific Aim 1: The main outcome is the difference in post-treatment improvement between children who receive high-dose VDS plus SU and those who receive solifenacin plus SU or SU monotherapy for OAB-dry symptoms. The study expects that high-dose VDS plus SU will lead to more improvement than SU monotherapy and solifenacin plus SU. Furthermore, SU monotherapy will result in less improvement than solifenacin plus SU.

Specific Aim 2: The secondary outcome is the safety profile of high-dose VDS plus SU for OAB-dry symptoms in pediatric patients. The study anticipates that the safety profile of high-dose VDS plus SU will be similar to that of solifenacin plus SU or SU monotherapy at follow-up.

The study design is an 8-week randomized controlled trial, and all treatments will be administered in a group setting. Pediatric patients with OAB-dry symptoms will undergo 8 weekly sessions of high-dose VDS plus SU, solifenacin plus SU, or SU monotherapy. Independent assessors will evaluate the patients before the treatment, at mid-treatment (4-week follow-up), and at the 8-week follow-up to test the expectations. To account for attention, time, and group effects, all SU sessions will be administered in a group setting.

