5. STUDY INTERVENTIONS

5.1 Interventions, Administration, and Duration

During the eight-week treatment period, the study was divided into three intervention groups, and each patient received follow-up care from an outpatient physician every four weeks. Participants in each intervention group will be required to attend a 30-minute SU program per session.

Children assigned to the VDS+SU group will receive high-dose VDS (800 IU, three times per day) in addition to the biweekly SU course.

Children in the SOL+SU group will receive treatment with solifenacin succinate (5 mg once daily, with a maximum dose of 10 mg per day), in addition to the SU course.

Participants in the SU group only attend regular SU meetings, which provide basic information and an explanation of the disease, guidance on behavioral changes and lifestyle advice, registration of urinary habits using a bladder diary, as well as support and encouragement from caregivers.

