7.1 Specification of Safety Parameters

Participants were required to take solifenacin and high-dose VDS as part of the study. Anticholinergic side effects, including dry mouth, blurred vision, constipation, and nausea, among others, may occur due to solifenacin use. If any of these symptoms occur, the medication will be discontinued, and the participant will be removed from the study. Over-supplementation of vitamin D can lead to symptoms of vitamin D toxicity, including anorexia, nausea, diarrhea, constipation, irritability, and somnolence. Any occurrence of these adverse drug reactions or serum vitamin D levels exceeding 100 ng/mL will be evaluated as unsafe.

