9.3.3 Safety analysis set

For safety analysis, which is when we assess the safety and side effects of the treatment, we will use the SS set, which is a subset of all patients who took at least one dose of the study drug and have safety records in the database. The database is where we store and manage our data electronically. We will only use measured values for this analysis, which are values that we actually observed and recorded for each subject. We will also do a sensitivity analysis using the PP analysis set, which is when we test how

robust our results are to different assumptions or scenarios.

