9.5.3 Safety analysis

The safety analysis will be performed using the Safety Analysis Set, which will assess treatment-emergent adverse events (TEAEs). Detailed recordings of all severe adverse events and TEAEs leading to discontinuation from the study will be included. Changes in clinical laboratory parameters and vital signs at each scheduled time point from baseline will be summarized according to treatment groups.

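### Aim 2 expects the safety of VDS+SU to be similar to that of both comparators, but Section 9.5.3 plans no between-arm estimate or interval, and the safety set read literally leaves out the SU arm.

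*Combined protocol and SAP*

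**What the plan says.** Section 9.1 makes safety the secondary outcome (Specific Aim 2). It anticipates that the safety profile of VDS+SU "will be similar to that of solifenacin plus SU or SU monotherapy at follow-up". It then says that independent assessors evaluate patients before treatment, "at mid-treatment (4-week follow-up), and at the 8-week follow-up to test the expectations". Similarity is therefore among the expectations that the trial says it will test.

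Section 9.5.3 is the planned safety analysis. Treatment-emergent adverse events (TEAEs) are assessed in the Safety Analysis Set. Severe events and TEAEs that lead to discontinuation are recorded in detail. Changes in laboratory values and vital signs "will be summarized according to treatment groups".

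Section 9.3.3 defines the safety set as "all patients who took at least one dose of the study drug and have safety records in the database" and adds a sensitivity analysis in the per-protocol set. Section 5.1 says of the third arm: "Participants in the SU group only attend regular SU meetings".

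For the continuous efficacy outcomes, Sections 9.5.1 and 9.5.2 plan between-group point estimates (or Hodges-Lehmann shifts) with 95% confidence intervals.

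**The concern.** Safety is in the trial's title and is its second aim. The section that serves this aim specifies no contrast between arms: no risk difference, interval, test or margin. The plan uses between-group intervals for continuous efficacy outcomes and does not carry them over to safety.

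The safety set adds a more basic gap. Aim 2 names SU monotherapy as a comparator, yet membership of the set depends on taking a study drug, and the SU arm is given none. On a literal reading that half of the comparison has nobody in the comparator arm.

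At stake is the support for whatever is said about Aim 2. With no planned contrast, a report has only the listed events and by-arm summaries to draw on, and two similar counts can be compatible with quite different true rates.

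**Working it through.** **The plan's own figure.** No sample size, precision or event rate is given for safety. The only calculation (Section 9.2) concerns voiding frequency: 87 per group, raised for 10% attrition. 87/0.9 = 96.7, so 97 per group, which agrees with the plan. These two values bracket the likely size of each arm in the safety analysis.

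**Assumptions.** Event rates of 5%, 10% and 20% and margins of 5, 10 and 15 points are assumed. Section 7.1 says only that anticholinergic effects "may occur due to solifenacin use".

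**Step 1. Interval for a risk difference when both arms show the same rate p.** The Wald half-width is 1.96 × √(2p(1−p)/n). With n = 97:

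- p = 5%: 1.96 × √(0.095/97) = 6.1 points
- p = 10%: 1.96 × √(0.18/97) = 8.4 points
- p = 20%: 1.96 × √(0.32/97) = 11.3 points

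The Wald form is too narrow when events are few, so the check was repeated with Newcombe's score interval. With equal counts its half-width is √((p−l)² + (u−p)²), where l and u are the Wilson limits for one arm. For 10/97, p = 10.3%, l = 5.7% and u = 17.9%, which gives √(4.6² + 7.6²) = 8.9 points.

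| Observed rate in both arms | Wald, n = 97 | Newcombe, n = 97 | Newcombe, n = 87 |
|---|---|---|---|
| 0 events | not informative | ±3.8 | ±4.2 |
| about 5% | ±6.1 | ±7.0 | ±7.2 |
| about 10% | ±8.4 | ±8.9 | ±9.5 |
| about 20% | ±11.3 | ±11.2 | ±11.8 |

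**Step 2. No events of a given type in one arm.** The exact two-sided 95% upper limit is 1 − 0.025^(1/n): 3.7% for 0/97 and 4.2% for 0/87.

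**Step 3. Chance that the interval excludes an excess of m points when the true rates are equal.** This is Φ(m/se − 1.96), with se = √(2p(1−p)/97), that is 3.1, 4.3 and 5.7 points at 5%, 10% and 20%.

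| True rate in both arms | m = 5 points | m = 10 points | m = 15 points |
|---|---|---|---|
| 5% | 36% | 89% | 99.8% |
| 10% | 21% | 64% | 94% |
| 20% | 14% | 41% | 74% |

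At these rates a 5-point excess would usually remain open. A 10-point excess would usually be excluded at a 5% rate, but not reliably at 10% or above. A 15-point excess would be excluded with high probability at rates up to 10%.

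**Step 4. The safety set against the arms.** Section 9.3.3 requires at least one dose of study drug. Section 5.1 gives VDS to one arm, solifenacin to another and SU sessions only to the third. The first two can qualify; read literally, the third cannot.

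**The case against.** Aim 2 says only that the study anticipates a similar profile. The trial was sized for voiding frequency and claims no power for safety, descriptive safety reporting is common, and nothing in Section 9.5.3 forbids reporting intervals. Much of this stands and limits the point. Three stronger readings should not be drawn.

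- A reader might infer that the trial will declare similarity from side-by-side counts or from a non-significant test. The documents do not say so. They give no rule for concluding similarity, and Section 9.5.3 contains no test that could be non-significant.
- A reader might infer that adverse events are merely summarised. The sentence on summaries by treatment group concerns laboratory values and vital signs. TEAEs are to be assessed, severe events recorded in detail, and a per-protocol sensitivity analysis run. None of these adds a between-arm estimate.
- A reader might infer that the counts cannot rule out any material difference. That depends on event rates and a margin that the documents do not give. For a 10-point margin at a 5% rate, or a 15-point margin at a 10% rate, the trial would probably exclude the difference.

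The objection also limits what a fix can do. Without a margin, an interval shows which differences remain compatible with the data, but cannot by itself establish that two profiles are similar. In addition, drug-related events have no clear meaning in an arm that receives no drug, and they will overlap with discontinuations because Section 8 ties the two together.

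What the objection does not answer is that an expectation said to be tested has no planned contrast, and that one of its two comparators is outside the analysis set as defined.

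**Conclusion.** The concern holds as a gap between Aim 2 and the safety analysis: no between-arm safety estimate or interval is specified, and the safety set literally excludes the SU arm. At 87 to 97 per arm, identical observed counts would leave open differences of about 6 to 7 points at a 5% rate, 8 to 9.5 at 10% and 11 to 12 at 20%. These sizes rest on assumed event rates, assumed equal in the two arms compared. The gap does not touch the primary outcome, and closing it needs no extra patients or data collection. It is a worthwhile improvement and not a threat to the trial.

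**What to change.** 1. In Section 9.3.3, define the safety set to include all randomised SU participants who started SU and have safety records, alongside the drug-arm patients who took at least one dose. Say what counts as treatment-emergent in the SU arm.
2. In Section 9.5.3, report the risk difference with a 95% confidence interval for VDS+SU against each other arm, for any TEAE, any serious adverse event and discontinuation for a TEAE. Use a score-type or exact method because events may be sparse. Compare drug-related TEAEs between the two drug arms only.
3. In Section 9.1, reword Aim 2 as estimating the safety difference, and state that conclusions are worded from the interval and not from side-by-side counts or a non-significant test. If the sponsor prefers to keep a claim of similarity, it needs a prespecified and justified margin, and the second table above shows that a narrow one would rarely be met.

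The cost is a few sentences and one extra table. The downside is that the safety conclusion may have to be worded more cautiously.

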9.2 Sample Size and Randomization

Before we design the current trial, we did a preliminary study with the support of the Program for Youth Innovation in Future Medicine at Chongqing Medical University. This was to check if we could do the trial successfully and recruit enough participants. We recruited children who were between 5 and 18 years old and who had symptoms of urgency and urinated at least 9 times per day as recorded in a 7-day diary. A diary is a tool where participants record their symptoms and behaviors over a period of time. They chose to whether receive either high-dose VDS plus SU therapy for eight weeks, which is our new intervention. The Department of Pediatric Urology at the National Center for Clinical Medical Research (Chongqing) collected bladder diaries from participants before and after the treatment to evaluate how well the treatment worked. The main outcome was the change in how often they urinated, and other outcomes that we measured were how severe their urgency was, how often they woke up at night to urinate, and how bad their symptoms were using the PLUTS score. The PLUTS score is a tool that measures different aspects of lower urinary tract symptoms in children.

We also measured how much their symptoms bothered them and how their healthrelated QoL was affected by their condition using the QoL score questionnaire. The QoL score is a tool that measures how satisfied participants are with their health and well-being. We also asked participants to rate how much they improved and how satisfied they were with the treatment using validated tools. The results of our preliminary study were positive and showed that our new intervention was promising. This encouraged us to continue with our main trial and test our intervention further. We created and finalized the study protocol, which is the document that describes the details and procedures of our study. We developed all data collection tools and forms, which are the tools and documents that we use to collect and record data from participants. We obtained IRB approvals at the National Clinical Research Center for Child Health and Disease (Chongqing, China), which are approvals from a committee that oversees the ethical aspects of our study and protects the rights and welfare of participants. We offered standard training to all coordinators and interventionists, who are the people who help us run the study and deliver the intervention to participants. Our preliminary data helped us to determine how many participants we needed for our main trial.

The primary outcome in our study will be the change in median voiding frequency from enrollment to 4-week follow-up and 8-week follow-up. In our previous feasibility study, the mean number of voids per day was 16.0 (SD, 5.0) at enrollment. We used the power analysis program PASS 15.0 to estimate the sample size of this randomized controlled trial. A sample size of 87 participants per group was needed to detect a difference of 1.5 voids per day between groups at the 0.05 level of significance, achieving more than 95% power, assuming an estimated SD of 5.0 after 8 weeks of treatment. We plan to recruit 97 participants per group, anticipating a 10% follow-up attrition, to ensure adequate power for the trial, for a total of about 300 participants. Our sample size estimations are supported by our previous trial.

Independent assessors will be kept blind to the treatment allocation throughout the study. Patients will receive a reminder script emphasizing the importance of not revealing their treatment information before the assessment. Randomization codes will be created by the study statistician before recruiting the first participant in the trial. Data analysis will not start until after the study's completion.

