9.5.1 Primary Outcome

The study aims to determine the primary outcomes of urinary frequency among three groups of participants. The frequency of urination will be recorded at three different points in time, i.e., when the participants enroll in the study, four weeks after starting the treatment, and eight weeks after starting the treatment. We will compare the frequency of urination between the groups at each time point, and assess changes in urination frequency from enrollment to four weeks after starting treatment. To record urinary frequency, we will use a bladder diary, and these outcomes will be considered continuous variables, with any positive integer value within a specified range.

To analyze the data, we will use the intention-to-treat approach to avoid bias from factors such as dropout or crossover. We will also handle missing data before analysis. Statistical tests will be applied to compare the groups based on data distribution and variance, which affects the reliability of results. For normally distributed data with homogeneous variance, we will use ANOVA, followed by post-hoc comparisons and Bonferroni correction to reduce Type I errors. We will report data changes using mean and SD and differences between groups using point estimation and 95% confidence intervals (95%CI).

For non-normally distributed data with heterogeneous variance, we will use the Kruskal-Wallis test to compare groups. Post-hoc comparisons between groups will be done using the Wilcoxon rank sum test, and p-values will be adjusted by Bonferroni correction. Data changes will be reported using median and IQRs, and differences between groups using the Hodges-Lehmann (HL) estimate of location shift and 95% confidence intervals (95%CI). P-values will also be adjusted for multiple comparisons to avoid false positives, and a two-tailed P-value less than .05 will be considered statistically significant.

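### Section 9.2 attaches more than 95% power to a 1.5-void difference between groups; with 87 per group and SD 5.0, a two-group contrast of that size has 50% power, or 33% after Bonferroni correction

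*Combined protocol and SAP*

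**What the plan says.** Section 9.2 (Sample Size and Randomization) states: "A sample size of 87 participants per group was needed to detect a difference of 1.5 voids per day between groups" at alpha 0.05, "achieving more than 95% power, assuming an estimated SD of 5.0 after 8 weeks of treatment". The software is named (PASS 15.0). The test, the three assumed group means and any multiplicity adjustment are not. Recruitment is set at 97 per group to allow for 10% attrition.

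The same section defines the endpoint: "The primary outcome in our study will be the change in median voiding frequency from enrollment to 4-week follow-up and 8-week follow-up". The feasibility figure it cites is a raw score: "the mean number of voids per day was 16.0 (SD, 5.0) at enrollment".

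Section 9.1, Specific Aim 1, sets out pairwise expectations: "The study expects that high-dose VDS plus SU will lead to more improvement than SU monotherapy and solifenacin plus SU", and "Furthermore, SU monotherapy will result in less improvement than solifenacin plus SU". Section 9.5.1 (Primary Outcome) plans an overall test and then pairs. For normal data with equal variances, "we will use ANOVA, followed by post-hoc comparisons and Bonferroni correction to reduce Type I errors"; otherwise Kruskal-Wallis, then Wilcoxon rank-sum tests with Bonferroni correction. Testing is two-tailed at 0.05.

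**The concern.** A difference of 1.5 voids against an SD of 5.0 is a standardised difference of 0.3. Detecting that between two groups with 95% power takes far more than 87 per group, so the sentence in 9.2 cannot be true of a single between-group contrast. It may be true of an overall three-group test, but the section does not say that this is what was calculated.

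The distinction matters because rejecting the overall null hypothesis establishes none of the three claims in Aim 1. Each rests on a Bonferroni-corrected pair. A reader who carries the 95% over to VDS+SU against SOL+SU could take a non-significant result as good evidence that no 1.5-void difference exists. If a true difference of that size were present, the corrected test would miss it about two times in three.

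**Working it through.** **Inputs.** From 9.2: n = 87 per group, difference 1.5 voids/day, SD 5.0, alpha 0.05, attrition 10%. From 9.5.1: two-sided tests, overall ANOVA, then Bonferroni-corrected pairs. The Bonferroni divisor is not stated; I take three pairs, so alpha = 0.05/3 = 0.0167.

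**1. Reproducing the plan's figure.** For a one-way ANOVA, the noncentrality is λ = n Σ(μᵢ − μ̄)²/σ², referred to F with 2 and 3(n − 1) degrees of freedom.

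| Assumed means | Σ(μᵢ − μ̄)² | λ at n = 87 | Power at n = 87 |
|---|---|---|---|
| 0 / 1.5 / 3.0 | 4.5 | 87 × 4.5/25 = 15.66 | 95.05% |
| 0 / 0 / 1.5 | 1.5 | 87 × 1.5/25 = 5.22 | 51.7% |
| 0 / 0.75 / 1.5 | 1.125 | 87 × 1.125/25 = 3.915 | 40.3% |

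For 0/1.5/3.0, n = 86 gives 94.8%, so 87 is exactly the smallest n reaching 95%. The attrition step also reproduces: 87/0.9 = 96.7, rounded up to 97.

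The overall F test depends only on Σ(μᵢ − μ̄)², so other patterns with a sum of 4.5 give the same power. If two groups are 1.5 apart, however, the third is fixed. With means 0, 1.5 and x, the sum is (2/3)(x² − 1.5x + 2.25). Setting this to 4.5 gives x² − 1.5x − 4.5 = 0, so x = 3.0 or −1.5. Both are equal 1.5-void spacing. Apart from rounding to a whole n, this is the only pattern with a 1.5-void gap that yields 87.

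**2. Power of one two-group contrast.** Noncentral t, δ = d/(σ√(2/n)), 172 degrees of freedom. For d = 1.5, δ = 1.5/(5 × √(2/87)) = 1.979, against a critical value of 1.974 (alpha 0.05) or 2.418 (alpha 0.0167).

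| True difference | Unadjusted | Bonferroni, three pairs |
|---|---|---|
| 1.5 | 50.3% | 33.3% |
| 2.0 | 74.6% | 58.8% |
| 2.5 | 90.6% | 81.0% |
| 3.0 | 97.6% | 93.7% |

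If all 97 per group were evaluable, the 1.5-void row becomes 54.7% and 37.4%. Reaching 95% power for a 1.5-void pair takes 290 per group unadjusted or 364 adjusted. At n = 87 the smallest difference detected with 95% power is 2.75 voids unadjusted or 3.09 adjusted.

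**3. What the inferred pattern implies.** With the ordering in Aim 1 and equal 1.5-void steps, VDS+SU against SU is a 3.0-void contrast (93.7% adjusted). VDS+SU against SOL+SU and SOL+SU against SU are 1.5-void contrasts (33.3% each).

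**4. Sensitivity to the SD.** Suppose 5.0 is the raw SD at both visits and the analysed outcome is change. Then SD of change = 5√(2(1 − r)), where r is the baseline-to-week-8 correlation. The documents do not give r, so this is an assumed range.

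| r | SD of change | 1.5 voids, unadjusted | 1.5 voids, adjusted |
|---|---|---|---|
| 0.3 | 5.92 | 38% | 23% |
| 0.5 | 5.00 | 50% | 33% |
| 0.7 | 3.87 | 72% | 56% |
| 0.8 | 3.16 | 88% | 76% |

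Power of 95% needs an SD of change of 2.73 unadjusted (r about 0.85) or 2.43 adjusted (r about 0.88).

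**The case against.** The best defence is that powering the overall test is a recognised choice and matches the order of analysis in 9.5.1, where the pairs come second. The exact match at 87 supports that reading, and I accept that the calculation itself may be sound. Section 9.2 still does not say so, and a 1.5-void difference between groups is not a fair description of means spanning 3.0 voids.

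Second, the mean pattern is not unique. Means of 0, 0 and 2.6 (exactly 2.598) give the same overall power at n = 87, and each VDS contrast would then have 92.6% power unadjusted and 84.2% adjusted. So the contrast-by-contrast figures in step 3 do depend on the inferred pattern. But 0/0/2.6 contains no 1.5-void gap and not the full Aim 1 ordering, so it does not fit 9.2. The 50% and 33% for a 1.5-void pair depend on no pattern at all.

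Third, the Bonferroni divisor is inferred. If only the two VDS comparisons counted, adjusted power for 1.5 voids would be 39.1%, still far from 95%.

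Fourth, 9.2 ties the SD to the end of 8 weeks, which reads as the spread of week-8 frequency, and 9.5.1 does compare raw frequency at each time point. That answers part of the SD question. It leaves a mismatch with an endpoint that 9.2 defines as a change.

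Finally, no rule in the plan requires all the pairwise claims to succeed together, so I draw no conclusion from joint power.

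**Conclusion.** The concern holds: the power statement is wrong as written. At the stated SD, alpha and group size, a 1.5-void contrast between two groups has 50% power, or 33% with Bonferroni correction over three pairs, against the stated figure of more than 95%. The 95% belongs to an overall ANOVA with means 1.5 voids apart. That pattern is inferred from the exact match at 87 and from the ordering in Aim 1, and only the PASS output can confirm it. If it is right, about 95% power applies to the overall test and nearly to VDS+SU against SU, but not to the other two Aim 1 comparisons.

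The pairwise figures assume normal data, equal groups and an SD of 5.0 for the variable analysed. A smaller SD of change could raise them, but the documents give none, and a correlation of about 0.85 or more would be needed. The planned 95% confidence intervals will show the imprecision in the results; they do not correct the power claim. This should be fixed, but it does not undermine the design.

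**What to change.** First confirm the inputs from the PASS output. Then restate 9.2 so that it:

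- names the test and gives the three assumed means;
- says whether the SD of 5.0 is for raw frequency at week 8 or for change from enrolment;
- limits the 95% figure to the overall test under those means;
- states the Bonferroni divisor and gives adjusted pairwise power.

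If the output confirms the inferred pattern, wording such as this would do:

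> With 87 per group, the overall three-group ANOVA (two-sided alpha 0.05, SD 5.0) has 95% power if the group means are 0, 1.5 and 3.0 voids/day. For one pairwise comparison at the Bonferroni level for three pairs (0.0167), power is about 33% for a difference of 1.5 voids/day, 81% for 2.5 and 94% for 3.0.

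A sentence should cover the rank-based branch of 9.5.1. Under normality (relative efficiency 0.955), overall power is about 94%, and an unadjusted 1.5-void pair has about 48%. If the analysed outcome is change and the feasibility data support a smaller SD of change, state that SD with its source and recompute.

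The cost is a rewording of 9.2 and a check of one software output. No extra patients are needed and the analysis is unchanged. The price is a less favourable stated power for the 1.5-void comparisons.

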6.2.2.3 Randomization

After completing a comprehensive baseline assessment and meeting the eligibility

criteria, eligible participants will be randomized into one of three different intervention groups. To ensure the highest standard of allocation concealment, the randomization process of this clinical trial will be executed by a designed computer program developed by a project staff member who is not involved in the execution and statistical analysis of this study. The allocation will be securely hidden in sequentially numbered sealed envelopes, which will be entrusted to an inpatient doctor who is not involved in the trial.

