6.2.3 Blinding

To minimize assessment bias and ensure the integrity of the study, we will implement rigorous measures to conceal group allocation and hypotheses from outcome assessors and statisticians. We will emphasize the importance of minimizing assessment bias to assessors and regularly review the blinding status to strictly maintain blinding. In addition, the data analyst will only be allowed to review coded data with participant names replaced by numbers.

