10.2 Data Management

The biostatisticians will manage the study database, while the principal investigators ([name]) will oversee the researchers and data management staff to ensure the quality and execution of the study. [name], MD, will supervise the data management and quality. The collected data will include various assessments, such as screening data, clinician- and patient-rated assessments, fidelity, visit adherence, and safety data, as well as interrater reliability and certification data. Weekly reports will track enrollment, completion, attrition, subject progress, and critical assessments. Baseline characteristics, protocol adherence, and other issues will be monitored using additional reports as necessary.

Data will be collected directly by patients and study staff through a QR code, which links to a website. The data will be exported to a relational database in Microsoft software for systematic querying and checking. Paper-based data will be entered by 2 independent staff members to prevent errors or missing data and verified by another staff member at the end of the study.

Monthly reports will monitor enrollment, completion, attrition, subject progress, and critical assessments. Additional reports will monitor baseline characteristics, protocol adherence, and other issues. Data will be de-identified using subject number, visit number, and date of visit to comply with local privacy requirements. Electronic data will be encrypted and password-protected, with only ID numbers being used to identify subjects. De-identified data will be transmitted for data analysis. Consent forms and hard copy protected health information will be kept in locked cabinets in a secure office.

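### Section 9.2 has the study statistician create the randomization codes, which contradicts the blinding of statisticians claimed in section 6.2.3, and nothing separates the code-maker from the analyst

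*Combined protocol and SAP*

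**What the plan says.** Three sections of the combined protocol and SAP deal with who knows the allocation.

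- Section 9.2 (Sample Size and Randomization): "Randomization codes will be created by the study statistician before recruiting the first participant in the trial". It adds: "Data analysis will not start until after the study" is complete.
- Section 6.2.2.3 (Randomization): allocation is produced by a computer program "developed by a project staff member who is not involved in the execution and statistical analysis of this study". The results go into "sequentially numbered sealed envelopes, which will be entrusted to an inpatient doctor who is not involved in the trial".
- Section 6.2.3 (Blinding): the trial will "conceal group allocation and hypotheses from outcome assessors and statisticians", and "the data analyst will only be allowed to review coded data with participant names replaced by numbers".

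Section 10.2 (Data Management) is also relevant: "The biostatisticians will manage the study database". No section names an unblinded statistician, and none states that the statistician who makes the codes is excluded from the analysis.

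**The concern.** The trial is observer-blind (section 3), so the blinding it claims lies mainly with the outcome assessors and the statisticians. If the person who makes the allocation list also analyses the data, the second of these is lost.

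That matters because the plan leaves several decisions open until the data are in hand:

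- Section 9.5 promises a check for outliers but gives no rule for acting on them. It promises multiple imputation but specifies no imputation model, and the missing-data sensitivity analysis is not described.
- Section 9.5.1 picks the primary test from the observed distribution and variance. It covers normal data with equal variances and non-normal data with unequal variances, and assigns no test to the two mixed cases.
- Section 9.3.2 sets per-protocol membership before database lock, partly on a judgement of whether a participant followed the protocol properly.

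Someone who knows the arms can lean one way on such choices without intending to.

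**Working it through.** No significance level, SD, effect size or sample size enters this point, so there is nothing to compute. The check is whether the statements about roles can all be true together.

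| Section | Task or property | Assigned to |
|---|---|---|
| 9.2 | Creates the randomization codes | Study statistician |
| 6.2.2.3 | Develops the randomization program | Staff member outside execution and analysis |
| 6.2.2.3 | Holds the sealed envelopes | Inpatient doctor outside the trial |
| 6.2.3 | Kept unaware of allocation | Outcome assessors and statisticians, no exception |
| 6.2.3 | Sees data with names replaced by numbers | Data analyst |
| 10.2 | Manages the database | Biostatisticians |

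**Step 1: 9.2 against 6.2.3.** Whoever creates the codes knows the sequence or can regenerate it. That person is a statistician, and 6.2.3 conceals allocation from statisticians generally. The two statements conflict directly.

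**Step 2: 9.2 against 6.2.2.3.** Here the conflict is conditional. Section 6.2.2.3 says who developed the program, not who ran it or kept its output. The outside staff member could have written the program and the statistician could have run it. The two sections clash only if creating the codes is taken to be part of what 6.2.2.3 gives to a non-analyst, and the study statistician is taken, in the ordinary sense, to be the analyst. Even on the milder reading, the statistician has had access to the list, and Step 1 is unchanged.

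**Step 3: do the other safeguards repair it?**
- Envelopes with an outside doctor protect assignment at enrolment. They do not remove knowledge from the person who made the sequence.
- Starting analysis after completion fixes the timing, not who knows the allocation.
- Replacing names with numbers hides who a participant is. It is not described as hiding the arm.

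**Step 4: what is exposed if the code-maker analyses?**
- Primary outcome and the other continuous outcomes: intention-to-treat (9.3.1, 9.5.1), so test choice, outlier handling and imputation.
- Categorical outcomes (rated improvement, and satisfaction with willingness to receive another therapy): per-protocol set (9.3.2, 9.5.2), so membership, if statisticians take part in deciding it.
- Safety: the per-protocol set serves only as a sensitivity analysis (9.3.3), on the same condition.

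**The case against.** The strongest reply is that the documents use different titles: a study statistician in 9.2, a data analyst in 6.2.3 and biostatisticians, in the plural, in 10.2. If the code-maker and the analyst are different people, the analyst may be blind and the harm does not arise. This is possible, and it limits what can be said about consequences. It does not remove the contradiction, because no section states the separation and 6.2.3 makes no exception for any statistician.

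Other parts of the reply stand and narrow the point:

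- A reader might infer that 6.2.2.3 already gives the creation and custody of the list to the independent staff member, so that 9.2, 6.2.2.3 and 6.2.3 are all mutually incompatible. The text of 6.2.2.3 goes only as far as developing the program.
- A reader might infer that the list ties each subject number in the database to an arm. Section 10.1 mentions a unique ID number but does not say that it follows the randomization sequence. The link is plausible, but it is an assumption.
- A reader might infer that per-protocol decisions touch the primary outcome. They do not, because that analysis is by intention to treat. Nor does the plan assign those decisions to the statistician: 9.3.2 names no role, and 10.3.2 has deviations reviewed with the principal investigator.
- The normality and variance rule narrows discretion over the test. It does not remove it, given the uncovered mixed cases and the lack of any outlier rule or imputation model.

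**Conclusion.** The inconsistency is real and lies in the current text. Sections 9.2 and 6.2.3 cannot both be followed as written. If 9.2 is followed, the claimed blinding of statisticians fails at least for the person who made the codes. It fails for the analysis too if that person performs it, which the documents neither state nor rule out.

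The size is one of scope, as set out in Step 4 of the working, and no shift in an estimate or error rate can be derived. The conclusion rests on one premise: creating the codes gives knowledge of the allocation or the means to reconstruct it.

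It would be tempting to go further and say that allocation concealment is broken, that assessors are unblinded, or that the results are biased. The documents support none of these. The envelopes stay with an outside doctor, assessor blinding is described separately and is untouched by this conflict, and opportunity for bias is not evidence of it.

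**What to change.** Replace the code-creation sentence in 9.2 so that it says:

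- the independent staff member of 6.2.2.3, who has no analysis role, generates the codes and keeps the list from the analysing statistician;
- the analyst works with masked group codes such as A, B and C;
- arm identities are released only after per-protocol membership, outlier handling, imputation and test choice are fixed and the database is locked.

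The last condition needs all of its parts. Releasing identities at lock alone would be too early: analysis starts after study completion, so outlier, imputation and test decisions could still follow the release. Section 6.2.2.3 should say in matching words that this staff member generates and holds the list, since it now mentions only the program.

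Masked codes have a practical limit. Follow-up serum vitamin D (6.2.4, 7.2) and study-drug records could reveal the arms, so these fields are best withheld until the decisions are fixed.

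If the statistician did in fact generate the codes, the protocol should say so, state that this person takes no part in the analysis, and assign the analysis to a different, blinded statistician.

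The cost is a short change of wording in 9.2 and 6.2.2.3. The first route needs no added staff, because the independent role already exists. The second needs a second statistician, and 10.2 refers to more than one. Nothing changes in sample size, visits or data collection.
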